12.3 MONITORING/ SOURCE DOCUMENT VERIFICATION.....	38
12.4 DATA CONFIDENTIALITY AND SECURITY.....	38
12.5 REPORTING SCHEDULE.....	39
12.6 RECORD RETENTION POLICY.....	39
12.7 OWNERSHIP OF DATA AND PUBLICATION POLICY.....	39
13. REFERENCES.....	40
14. STUDY ACKNOWLEDGEMENT.....	42
15. APPENDIX 1 – TERMS OF REFERENCE.....	43
15.1 STEERING COMMITTEE.....	43
15.2 STUDY MANAGEMENT COMMITTEE.....	43
16. APPENDIX 2 – INFORMED CONSENT PROCEDURES AND FORMS.....	44
16.1 INFORMED CONSENT.....	44
17. APPENDIX 4 – PROPOSED REFORM INTERVENTION TIMELINE.....	47
18. APPENDIX 5 - DECLARATION OF HELSINKI.....	48
19. APPENDIX 6 – SUMMARY OF PROTOCOL AMENDMENTS.....	53

1. Overview

Title of study: Supporting Companies to Reform Nutrition Policies and Practices (REFORM)

Investigators and study centres

This study has been designed by independent investigators at the National Institute for Health Innovation (NIHI), University of Auckland, New Zealand, the Global Obesity Centre (GLOBE), Institute for Health Transformation (IHT), Deakin University, Australia, and The George Institute for Global Health (TGI), Australia. The overall design and conduct of this trial are the responsibility of the Principal Investigators and members of the Study Management Committee. The study will be co-ordinated jointly by NIHI and GLOBE.

Study period: July 2020 – June 2024

Objectives: The primary objective of this trial is to determine the effects on the nutrient profile (Health Star Rating) of food company product portfolios, of the provision of tailored support to companies on their nutrition-related policies and practices (food composition, nutrition labelling, marketing to children, food accessibility), compared to food companies that are not offered the programme (the control).

Duration of intervention: 12 months

Study design and methodology: The REFORM study is a parallel, two-arm, cluster randomised controlled trial. Food companies serving as the clusters will be randomly assigned (2:1 ratio) to receive either a tailored support intervention programme or no intervention. Randomisation will be stratified by country (Australia, New Zealand), industry sector (chained consumer food services, other packaged food/non-alcoholic beverage companies), and company size (greater than or equal to median category revenue, less than median category revenue). All companies will be followed for 24 months, with outcome assessments at baseline, 12 months, and 24 months.

Study population: Eligible companies will have Australia- and/or New Zealand-based production operations of foods or non-alcoholic beverages, and a product portfolio of at least 10 products where reformulation is considered by the research team to be feasible. Companies will be identified using the Euromonitor Passport database and cross-checked against the Australian FoodSwitch and New Zealand Nutritrack databases, to ensure annually updated food composition and labelling data are available for identified companies.

Sample size: A total of 150 food companies (intervention n=100, control n=50) across both countries.

Main criteria for inclusion

- A company involved in the production of food and/or non-alcoholic beverages
- >\$10 million in annual retail sales revenue
- Holding Company or Head Office and manufacturing located in Australia or New Zealand
- Product portfolio of at least 10 products considered amenable to reformulation

Exclusion criteria

Companies will be excluded if:

- They manufacture chewing gum products, sports supplements, or infant formula *only*
- They are currently engaged with the research team on similar interventions
- They are supermarkets or retailers/distributors/importers/wholesalers only
- Their product nutrition information is not available in the Nutritrack, or FoodSwitch databases and therefore nutritional profile and HSR is unable to be assessed.

Criteria for evaluation*Primary outcome*

The primary outcome will be the nutrient profile (measured using the Health Star Rating (HSR) system) of the foods and beverages produced by the food companies at 24 months post-baseline.

Secondary outcomes that will be measured are:

- Nutrient profile (measured using the HSR system) of the foods and beverages produced by the food companies at 12 months post-baseline
- Nutrient content (including sodium, sugar, and saturated fat) of the foods and beverages produced by the food companies at 12- and 24 months post-baseline
- Display of HSR labels on packaged foods and beverages produced by the food companies at 24 months post-baseline
- Company nutrition-related policies and commitments at 24 months post-baseline, measured using the validated Business Impact Assessment-Obesity and population nutrition (BIA-Obesity) tool
- Company engagement with the intervention and reported enablers and barriers to change
- Cost-effectiveness of the intervention and modelled impact on population health

Statistical methods*Study power*

A total of 150 companies (intervention n=100, control n=50) across both countries, with a minimum of 10 products per company, will provide 90% power at a 5% level of significance to detect a minimum 0.48-unit difference between groups in the mean HSR of all packaged food products over the 24-month follow-up period, assuming a mean HSR of products of 2.95, a standard deviation (SD) of 1.25, and an intra-cluster correlation (ICC) between products produced by the same company of 0.4. This would constitute an approximate 16% increase in the star rating (healthiness) of foods produced by the intervention companies compared to foods produced by the control group companies.

We estimate that about half of the intervention companies will participate in the intervention programme, which will reduce the effective sample size. A total of 100 companies (50 intervention and 50 control companies) will provide 80% power to detect the expected effect size on the primary outcome under the same assumptions.

Statistical analysis

Trial analyses will be conducted on an intention-to-treat (ITT) basis, following the CONSORT 2010 statement guidance with extension to cluster randomised trials. All randomised companies will be included in the primary ITT analysis. A per-protocol (PP)

analysis will also be conducted including only those intervention companies that participate in the intervention programme as per protocol.

Descriptive information will be presented at both company and food category level by treatment group pre- and post-intervention. Primary and secondary efficacy outcomes will be tested between intervention and control groups using generalised linear mixed models. The fixed effects will include treatment group, stratification factors, baseline outcome value and key food categories. Food company will be included as a random cluster effect. The ICC coefficients will be estimated using the trial data. The size of any intervention effect will be estimated overall and by key food categories. Country-level analysis will also be undertaken.

The extent to which companies engage with the intervention and the ways in which intervention activities influence company activities will be assessed via a comprehensive process evaluation, guided by theoretically and evidence-based programme logic of intervention pathways of effect and outcomes. The process evaluation will use a convergent mixed methods approach using pre-post surveys and post-intervention semi-structured interviews with company representatives to examine changes in company prioritisation, motivation, mechanisms, and resources for making nutrition-related policy and practice changes.

If the intervention is successful in changing the primary outcome, an economic evaluation will be conducted to assess its cost-effectiveness (cost per change in HSR). The longer-term population health impact of changes in HSR (cost per Health-Adjusted Life Year gained) will also be modelled. If the intervention is not successful, a costing analysis will be undertaken instead. All economic outputs will be reported with 95% uncertainty intervals, and selected scenario and sensitivity analyses will be undertaken to test the impact of important assumptions (including intervention reach and industry costs) on cost-effectiveness results.

Funding

This project is funded by the Health Research Council of New Zealand, the Australian National Health & Medical Research Council, the Victorian Health Promotion Foundation (VicHealth) and the Australian Government Department of Health (DoH).

2. Study Plan Schematic

Intervention group (n=100)

Control group (n=50)

Development of
study methods
Commencing 2020

Study design, company identification and randomisation, engagement strategy, recruitment

Intervention
Staggered 12-
month intervention
commencing
2021

1. **Provision of resources:** show companies how they rate against proposed awards/recognition programme criteria and competitors (using FoodSwitch & Nutrtrack data, and BIA-Obesity policy assessments), and support companies to improve performance using best practice exemplars, workshops, and other resources.
2. **Broker relationships:** provide information on third party service providers to support policy and practice improvements.
3. **Awards/recognition programme:** engage companies to have input into development of an accreditation programme, and facilitate consumer insights research on an accreditation programme

No intervention

Evaluation
Commencing 2023

Outcome Evaluation: Change in average HSR, average product nutrient content, and display of nutrition labelling (Nutrtrack, FoodSwitch), and company policies (BIA-Obesity)

Process Evaluation: Change in processes, priorities, motivation, mechanisms, and resources (post-intervention surveys & interviews)

Economic Evaluation: Within-trial cost effectiveness analysis and modelled scaled up analysis incorporating health impacts

3. Background

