6.11 Secondary outcome measures

The following secondary outcome measures will also be collected and assessed:

- Nutrient profile (measured using the HSR system) of the foods and beverages produced and sold by participating food companies at 12-months post-baseline.
- Nutrient content (including sodium, sugar, and saturated fat) of the foods and beverages produced by the food companies at 12- and 24 months post-baseline. The nutrient data will be extracted from the New Zealand Nutritrack and Australian FoodSwitch databases.
- Display of HSR labels on packaged foods and beverages produced by the food companies at 24 months post-baseline.
- Company nutrition-related policies and commitments at 24-months post-baseline, measured using the validated BIA (Business Impact Assessment)-Obesity tool (22). Publicly available data related to company policies and commitments to improve population nutrition will be assessed at baseline. Surveys (control and intervention companies) will be used to collect data at 24 months post-baseline. Policy areas include product formulation, product labelling, marketing to children and accessibility (price and availability) of healthy and unhealthy food.
- Company engagement with the intervention and reported, mechanisms, enablers, and barriers to improving nutrition-related policies and practices will be measured via the process evaluation interviews and surveys. Data collection for intervention food companies will occur via survey at baseline and 24 months post-baseline. Control companies will receive a survey at 24 months post-baseline only. Representatives from selected intervention and control companies will be invited to participate in in-depth interviews at

24 months post-baseline. Key indicators will be change relative to baseline in company prioritization and motivation for change, and change mechanisms and resources.

- Information on resources used to develop the awards/recognition programme, implement the intervention, and those accrued by intervention companies will be collected using resource use questionnaires. Resource use data and the primary outcome estimate will be used to conduct a within-trial cost-effectiveness analysis and a modelled analysis incorporating the population health impact of the intervention.

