Resource use associated with the co-production components of the intervention and collected from intervention companies will be assumed to represent the incremental costs for the intervention. At 24 months post intervention, the control companies will also be asked (during the process evaluation in-depth interviews and questionnaire) about relevant actions taken to improve nutrition related policies and practices over the last 24 months and associated resource use. Resource use data analysis will be completed on an ITT basis and complemented with a per protocol (PP) analysis. These will be reported as the numbers of observations, means, standard deviations (SD), medians and ranges. Both the within-trial and modelled cost-effectiveness analyses will use the treatment effects reported using the ITT and PP analyses. Any uncertainty associated with resource use and treatment effects will be accounted for using Monte-Carlo simulations (using the Microsoft Excel add-in Ersatz (34)) and all results will be presented with 95% uncertainty intervals. A detailed economic evaluation protocol will be developed and agreed upon by the Steering Committee.

7.2.4 *Procedures to account for missing data*

We do not anticipate missing data for the primary outcome, which will be measured independently using the Australasian Health Star Rating (HSR) nutrient profiling system applied to the foods and beverages produced and sold by the food companies included in the study. The nutrient data to estimate HSR will be extracted from the New Zealand Nutritrack and Australian FoodSwitch databases directly, both of which contain annually updated Nutrition Information Panel values, ingredients, and labelling information for packaged products available for sale in major supermarket stores in each country.

Generalised linear mixed models will also take into account any missing data at the product level using maximum likelihood methods, assuming they are missing at random.

Missing resource use data will be handled using various methods and guided by the most likely mechanism for missing data (e.g., data missing at random, covariate dependent missing etc.) (35).

7.2.5 *Interim analyses*

No interim analysis will be undertaken during the trial. All analyses will be conducted following completion of the 24-month intervention period.

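### The Overview makes the cost-effectiveness analysis conditional on an undefined successful primary result, other sections plan it unconditionally, and the use of control resource data in the incremental cost is not stated.

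*Protocol*

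**What the plan says.** Section 1 (Overview, Statistical analysis) sets a condition: cost per unit of HSR change is evaluated when the programme has succeeded on the primary outcome. It then gives the alternative: "If the intervention is not successful, a costing analysis will be undertaken instead". Nothing says what counts as successful.

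Elsewhere the analysis carries no condition:

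- The secondary outcomes in the Overview include "Cost-effectiveness of the intervention and modelled impact on population health".
- The schematic in section 2 lists a within-trial cost-effectiveness analysis and a modelled analysis.
- Section 6.11 states: "Resource use data and the primary outcome estimate will be used to conduct a within-trial cost-effectiveness analysis".
- Section 7.2.3 states: "Both the within-trial and modelled cost-effectiveness analyses will use the treatment effects reported using the ITT and PP analyses".

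On cost, section 7.2.3 says that resource use from the co-production components and from intervention companies "will be assumed to represent the incremental costs for the intervention". The next sentence has control companies asked at 24 months about "relevant actions taken to improve nutrition related policies and practices over the last 24 months and associated resource use". Table 1 in section 6.12 also schedules control companies' actions. No section says how the control data enter the incremental cost. Section 7.2.3 leaves detail to a separate economic evaluation protocol.

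**The concern.** There are two separate problems.

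**The condition.** A listed secondary outcome is promised in four places and made dependent on the primary result in a fifth. If the Overview sentence governs, an unsuccessful primary result removes the cost-effectiveness estimate, and a successful one yields an estimate built on an effect that had to be large to be reported. The planned 95% uncertainty intervals and Monte-Carlo simulation describe sampling uncertainty around the reported effect. They do not correct for selecting it.

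**The cost.** The effect is a difference between arms. A company-side cost taken from the intervention arm alone is not, so the ratio would set a gross cost against a net effect. Control companies may incur such costs: section 6.7 leaves both arms free to join other programmes, and section 3.3 describes reformulation support that already exists.

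At stake is the figure a funder would use to decide whether to keep the programme going. The primary analysis is not affected.

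**Working it through.** **Inputs** (sections 1 and 7.1, with sidedness from 7.2.2): SD 1.25; ICC 0.4; at least 10 products per company; 100 intervention and 50 control companies; difference 0.48; two-sided 5% level; about half of intervention companies expected to participate.

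**1. Reproduce the stated power.**
- SD of a company mean = 1.25 × √[(1 + 9 × 0.4)/10] = 1.25 × √0.46 = 0.848.
- SE of the difference, 100 v 50 = 0.848 × √(1/100 + 1/50) = 0.1468. Power for 0.48 is 90.5% (90.1% with a t reference), against 90% stated.
- SE, 50 v 50 = 0.848 × √(1/50 + 1/50) = 0.1696. Power is 80.8% (80.0% with t), against 80% stated.

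Both stated figures reproduce, so 0.1468 is the SE implied by the sample-size inputs. The protocol does not itself state an SE.

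**2. Effect of reporting only after success.** Assume that success means a significant positive ITT result. The estimate must then exceed c = 1.96 × 0.1468 = 0.288. For a true effect d, with a = (c − d)/SE, the mean estimate given success is d + SE × φ(a)/[1 − Φ(a)].

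For d = 0.24: a = 0.326, φ(a) = 0.378, 1 − Φ(a) = 0.372, so the mean is 0.24 + 0.1468 × 0.378/0.372 = 0.389.

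| True ITT effect | Chance of success | Mean estimate given success | Ratio to truth |
|---|---|---|---|
| 0.48 | 90% | 0.507 | 1.06 |
| 0.36 | 69% | 0.435 | 1.21 |
| 0.24 | 37% | 0.389 | 1.62 |

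The value 0.24 is 0.48 × 0.5: the design effect diluted by the expected participation, assuming no effect in companies that do not participate.

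**3. Sensitivity to baseline adjustment.** Section 7.2.2 adjusts for the baseline outcome. The protocol gives no baseline-to-follow-up correlation, so a range of company-level values r is assumed, with SE × √(1 − r²). At a true effect of 0.24:

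| r | SE | Chance of success | Ratio to truth |
|---|---|---|---|
| 0 | 0.147 | 37% | 1.62 |
| 0.5 | 0.127 | 47% | 1.45 |
| 0.8 | 0.088 | 78% | 1.14 |
| 0.9 | 0.064 | 96% | 1.02 |

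**4. Effect on the ratio.** Dividing a fixed cost by the mean selected effect at 0.24 and r = 0 gives 0.24/0.389 = 0.617, about 38% too low. Averaging the ratio itself over successful trials gives about 36% too low at r = 0 and 7% at r = 0.8. At a true effect of 0.48 and r = 0, the averaged ratio is 1.005 times the truth, so there is practically no bias.

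**5. Cost not netted.** If control cost is a share f of intervention-arm cost, the cost ratio is overstated by 1/(1 − f). The protocol gives no costs, so f is assumed: 0, 0.10, 0.25 and 0.50 give 1.00, 1.11, 1.33 and 2.00.

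**The case against.** The strongest reply has five parts.

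- **Only one Overview sentence imposes the condition.** If sections 6.11 and 7.2.3 govern, there is no selection. This stands. A reader might infer that every cost per HSR unit from this trial will rest on a selected effect, but the document does not support that. It supports a contradiction and a consequence if one side of it is followed.
- **The largest figure is a worst case.** It needs success to mean significance, no gain from baseline adjustment, and an effect fully diluted by non-participation. This stands too; at the design effect the bias is small.
- **Programme delivery costs are incremental by design.** Control companies are not contacted or offered the programme, so netting matters only for company-side costs. The control data are collected and nothing rules out subtracting them. A reader might infer that reported costs will certainly be un-netted, but the document only leaves the use of control data unstated, beside an assumption that points the other way. The Overview's planned sensitivity analyses on industry costs may also touch this component.
- **Detail is deferred to an economic evaluation protocol.** That can cover methods. It does not cure a conditional rule and an incremental-cost assumption that this document states itself.
- **If the test fails, the HSR difference and the costs are still reported with intervals.** This is correct. What is lost is their joint analysis, which is the listed secondary outcome.

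**Conclusion.** The contradiction between the Overview and the other sections is plain on the page and has to be resolved. If the Overview condition is kept, the effect entering the cost-effectiveness analysis is overstated on average by about 6% at a true effect of 0.48, 21% at 0.36 and 62% at 0.24. These figures assume that success means a significant positive ITT result and use an unadjusted SE of 0.147; baseline adjustment would reduce them, possibly to very little. In the 0.24 case without adjustment, the analysis would not be run about 63% of the time (100% − 37%).

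The incremental-cost statement in section 7.2.3 is a separate and smaller defect. It concerns company-side costs only, and its size depends on a control share that the protocol does not give. Selection tends to make cost per HSR unit look too low, and un-netted cost makes it look too high, so the net direction is unknown. The point is worth correcting because the remedy is cheap.

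**What to change.** 1. Delete the success condition in the Overview, so that it agrees with sections 2, 6.11 and 7.2.3. Run the within-trial cost-effectiveness analysis whatever the primary result.
2. Carry the full ITT effect distribution, including values at or below zero, through the planned Monte-Carlo simulation. Show the joint uncertainty in cost and effect rather than only a ratio, which is unstable when the effect is near zero.
3. Apply the same rule to the modelled analysis of cost per health-adjusted life year, or label that analysis as conditional on a positive result. Leaving it conditional without a label would keep the same selection there.
4. In section 7.2.3, define incremental cost as programme delivery cost plus the intervention-minus-control difference in company-side resource use, using the 24-month data already scheduled.

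The cost is revised wording and a little more analysis. The main drawback is that control resource data may be incomplete; section 7.2.4 already plans methods for missing resource-use data.

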3.1 Burden of diet-related disease

Unhealthy diets and excess body weight are leading contributors to poor health in Australia and New Zealand (NZ) (1, 2). Less than 7% of Australians consume diets that are consistent with the Australian Dietary Guidelines, and at least 35% of the energy intake of adults and up to 41% of the energy intake of children comes from ‘less healthy’ food and drinks (3). Two in three Australian adults and one in four children are overweight or obese (4). In NZ, the prevalence of overweight and obesity is similar in adults (65%) but higher in children (31%) (5). The high prevalence of obesity and diet-related disease has a high cost to the economy, including large impacts on the health care system and productivity (6).

